8.4.6.5 Safety Monitoring Plan

Subject safety will be routinely monitored as defined in Amgen's safety surveillance and signal management processes.

8.4.6.6 Other Safety Findings/Special Situations

All medication errors, misuse or abuse of the investigational product when associated with a serious adverse event must be reported to Amgen or designee immediately and no later than 24 hours of the investigator's awareness by collecting and recording the Other Safety Findings (OSF)/Special Situations (SS) event on the Clinical Trial electronic serious adverse events Contingency Report Form and submitting the form to Amgen Global Patient Safety or designee. Further details and definitions regarding OSF/SS - medication errors, misuse, or abuse, can be found in Section 11.4.

8.4.6.7 Pregnancy and Lactation

Details of all pregnancies and/or lactation in female subjects and, female partners of male subjects will be collected after the start of study treatment and until **60** days and **60** days, respectively, after the last dose of tarlatamab (Note: details of pregnancies and/or breastfeeding requirements for SOC therapies are based on regional prescribing information).

If a pregnancy is reported, the investigator is to inform Amgen immediately and no later than 24 hours of learning of the pregnancy and/or lactation and is to follow the procedures outlined in Section 11.5. Amgen Global Patient Safety will follow-up with the investigator regarding additional information that may be requested.

Abnormal pregnancy outcomes (eg, spontaneous abortion, fetal death, stillbirth, congenital anomalies, and ectopic pregnancy) are considered serious adverse events.

Further details regarding pregnancy and lactation are provided in Section 11.5.

Pregnancy Testing

A serum pregnancy test should be completed at screening within 7 days of C1D1 and serum or urine test completed on day 1 of each cycle, at EOT, and at SFU for females of childbearing potential (Section 1.3). During study treatment, all pregnancy tests completed at day 1 of each cycle need to be performed and reviewed before treatment administration. During LTFU, additional pregnancy testing should be performed **60** days after last dose of tarlatamab (Section 1.3). For subjects receiving SOC, refer to the regional prescribing information and/or local guidelines.

[figure not shown]
Note: Females who have undergone a bilateral tubal ligation/occlusion should have pregnancy testing per protocol requirements. (If a female subject, or the partner of a male subject, becomes pregnant it must be reported on the Pregnancy Notification Form, see [Figure 11-2](#)). Refer to Section [11.5](#) for contraceptive requirements.

Additional on-treatment pregnancy testing may be performed at the investigator's discretion or as required per local laws and regulations.

8.5 Pharmacokinetic Assessments

All subjects randomized to tarlatamab will have PK samples assessed.

Blood samples will be collected for measurement of serum concentrations of study treatment as specified in [Section 1.3](#). Blood must not be drawn from a port catheter during investigational product infusion and must be collected within 30 minutes after end of infusion prior to PK sample collection. If a permanent central line with more than 1 lumen is used, blood draws can be done via the lumen that is not used for drug administration. However, the preference is for PK samples to be drawn peripherally. The actual date and time (24-hour clock time) of each sample will be recorded.

8.7 Antibody Testing Procedures

All subjects randomized to tarlatamab will have blood samples collected for antibody testing.

Blood sample(s) for antibody testing are to be collected according to the time points specified in [Section 1.3](#) for the measurement of anti-tarlatamab binding antibodies.

Samples testing positive for binding antibodies will also be tested for neutralizing antibodies.

Refer to the Schedule of Activities (Section 1.3), as applicable, for specific time points, and the laboratory manual for detailed collection and handling instructions. More frequent antibody testing or testing for a longer period of time may be requested in the event of safety-related concerns.

8.8 Biomarkers

Biomarkers are objectively measured and evaluated indicators of normal biologic processes, pathogenic processes, or pharmacologic responses to a therapeutic intervention.

8.8.1 Biomarker Assessment During the Study

Tumor Tissue

[REDACTED]

[REDACTED]

[REDACTED]

[REDACTED]

[REDACTED]

[REDACTED]

[REDACTED]

Blocks are preferred, if available, but in lieu of blocks, unstained slides **can be submitted**. Block return may not be possible in every country. The tumor specimen submitted should be of sufficient quantity to allow for immunohistochemistry, DNA, and transcriptional analysis and include the corresponding pathology report; see the laboratory manual for details.

[figure not shown]
At end of treatment, fresh tissue samples will be collected after informed consent. These samples should be obtained following local standard practice that pose minimal risk to the patient (including investigator assessment of subject condition to undergo biopsy procedure).

[REDACTED]

[REDACTED].

When permitted by local regulations, blood and tumor tissue samples are to be collected and assessed for at the time points specified in the Schedule of Activities (Section 1.3):

Blood Samples

8.8.1.1 Biomarker Development

Samples will also be collected to develop or address biomarker hypotheses related to tarlatamab activity. These samples will also be used for developing methods that enable better understanding of the disease.

8.8.1.2 Biomarker Future Research

In oncology, there is particular interest in the molecular changes underlying the oncogenic processes that may identify cancer subtypes, stage of disease, assess the amount of tumor growth, or predict disease progression, metastasis, and responses to investigational product(s) or noninvestigational product(s)/auxiliary medicinal product(s).

If consent is provided by subjects, any remaining samples collected at the time points specified in the Schedule of Activities (Section 1.3), including samples collected for

biomarker assessments may be used for future research as described in Section [11.6](#).

No additional samples will be collected for future research.

Amgen or another third-party manufacturer may attempt to develop test(s) designed to identify subjects most likely to respond positively or negatively to tarlatamab or non-investigational product(s)/auxiliary medicinal product(s) to investigate and further understand SCLC.

8.9 Medical Resource Utilization and Health Economics

Medical Encounters

Medical resource utilization data, associated with medical encounters will be collected on the CRF by the investigator and study-site personnel for all subjects throughout the study. protocol-required procedures, tests, and encounters are excluded from the analysis of medical resource utilization and health economics.

The data collected may be used to conduct medical resource use analyses and will include:

- Number and duration of hospitalization (total days or length of stay, including duration by wards eg, intensive care unit)
- Number and type of diagnostic and therapeutic tests and surgical and nonsurgical procedures
- Reason for hospitalization (eg, adverse event such as CRS/ICANs or other)

Cytokine Release Syndrome

Medical resource utilization and health economics data, related to CRS, will be collected in the eCRF by the investigator and study-site personnel for all subjects throughout the study. protocol-required procedures, tests, and encounters are excluded from the analysis of health resource utilization and health economics.

The data collected may be used to conduct economic analyses and may include hospitalizations (by ward), concomitant medications, diagnostic and therapeutic tests and procedures related to CRS.

9. Statistical Considerations

9.1 Statistical Hypotheses

[figure not shown]
The hypotheses of the primary efficacy endpoint OS, key secondary efficacy endpoint PFS, and key secondary PRO endpoints will be tested. The OS endpoint will be tested with [REDACTED] overall type I error (alpha) of [REDACTED]. If OS is significant, the key secondary

efficacy endpoints of PFS and selected PRO endpoints can be tested sequentially in this order.

If both hypotheses of OS and PFS are rejected, the next 3 endpoints of change from baseline over time to week █ in 3 lung cancer symptoms including chest pain, cough, and dyspnea will be tested using Holm's procedure as illustrated in [Figure 9-1](#).

Hypotheses are rejected sequentially based on the smallest p-value.

[figure not shown]
Figure 9-1. Holm's Procedure for Change from Baseline Over Time to Week █ in 3 Lung Cancer Symptoms

dysp = dyspnea; pain = chest pain

If all 3 hypotheses listed above are rejected, the next 2 PRO endpoints will be tested using the Holm's procedure as illustrated in [Figure 9-2](#), including change from baseline over time to week █ in physical functioning and global health status. Hypotheses are rejected sequentially based on the smallest p-value.

Figure 9-2. Holm's Procedure for Change from Baseline Over Time to Week █ in Physical Functioning and Global Health Status

phys = physical functioning; ghs=global health status

9.2 Sample Size Determination

Approximately █ subjects per arm, total of approximately █ subjects will be enrolled.

Overall Survival:

A total of [] OS events will provide []% power to demonstrate superiority at an alternative HR of [] with log-rank test using [] overall type I error of [] in a group sequential design with [] interim analysis and [] primary OS analysis. Under exponential assumption, assuming that the SOC mOS is [] months (Spigel et al, 2021), a HR of [] reflects a []-month improvement in OS of the tarlatamab arm over SOC arm. The interim analysis is triggered at the time when []% ([] OS events occur. The dropout rate is anticipated to be []% per year assuming an exponential distribution.

With an enrollment rate of [] subjects per month and a []-month ramp-up period [] [] subjects per month for the first [] months), it is estimated that the OS interim and primary analyses occur at approximately [] and [] months respectively.

Progression-free Survival:

The analyses of PFS will occur once OS endpoints can claim statistical significance and will only be tested once.

9.3 Populations for Analysis

The following populations are defined:

Population	Description
ITT analysis set	All randomized subjects. All subjects will be analyzed according to the randomized treatment arm. The ITT analysis set will be used for primary and secondary efficacy endpoints, unless specified otherwise.
Safety analysis set	All subjects who take at least 1 dose of study treatment. Subjects will be analyzed according to the study treatment they actually received.

9.3.1 Covariates

Covariates may be incorporated in selected models of efficacy endpoints. In addition to the stratification factors for randomization, the following additional covariates may be included:

- region (North America and Europe vs rest of world)
- best response on last prior therapy
- age (< 65 years vs \geq 65 years)
- sex (male vs female)
- race (white, black, Asian, other)
- liver metastasis at baseline

- disease stage at initial diagnosis
- smoking history
- baseline ECOG
- baseline LDH

9.3.2 Subgroups

In addition to the stratification factors for randomization, primary and selected secondary endpoints may be examined in the following subgroups to investigate the consistency of treatment effects:

- region (North America and Europe vs rest of world)
- age (< 65 years vs \geq 65 years)
- sex (male vs female)
- race (white, black, Asian, other)

[REDACTED] . The analyses of biomarkers may be performed after collection of all samples during the conduct of the study and therefore may be reported after the primary analysis of efficacy endpoints.

9.4 Statistical Analyses

The SAP will be developed and finalized before database lock. Below is a summary of the timing and methods for the planned statistical analyses. To preserve study integrity, the final analysis will be conducted and reported following the end of study, as defined in Section 4.5.

9.4.1 Planned Analyses

9.4.1.1 Interim Analysis and Early Stopping Guidelines

A description of the interim analysis and primary analysis is listed in [Table 9-1](#). An average accrual rate of [REDACTED] subjects per month with a [REDACTED]-month ramp-up period is assumed. Depending on the actual enrollment rate, the number and timing of interim analyses could be different from what is projected here.

Table 9-1. Purpose and Timing of the Planned Analyses

Timepoint	Adaptive Decision and Analysis Scope	Number of subjects or events	Timing
IA █% OS)	Efficacy/Safety	Total of █ OS events from both tarlatamab and SOC arm (the study is █ months fully enrolled)	█ months
OS PA	Efficacy/Safety	Total of █ OS events from both tarlatamab and SOC arm	█ months

IA = interim analysis; ORR = objective response rate; OS = overall survival; PA = planned analysis; SOC = standard of care.

An independent (external to Amgen) DMC will review unblinded interim safety and efficacy data as per DMC charter. The safety interim assessment from this committee will be approximately every 6 months afterward. If any safety interim is within 2 months of the IA, they may be combined.

Additionally, Amgen Pharmacovigilance conducts ongoing safety monitoring of blinded data throughout the clinical study.

Interim Efficacy Rules:

The testing of OS at the interim and primary analyses is adjusted using the Lan-DeMets alpha spending function with an O'Brien-Fleming approach. [Table 9-2](#) shows the efficacy boundaries, which if crossed will enable claiming of OS efficacy. Data will be subject to ongoing checks for integrity, completeness, and accuracy in accordance with the Data Management Plan with the expectation that outstanding data issues are resolved ahead of the lock to the extent possible. The data supporting the interim analysis will be locked to prevent further changes.

Table 9-2. Stopping Boundaries of OS

Analysis	Information Fraction	Cumulative Events	Alpha spending	p-value (primary inference)	HR boundary
Interim					
Primary					

HR = hazard ratio; OS = overall survival.

9.4.1.2 Primary Analysis

The timing for the Primary Analysis (PA) of OS will be event driven and will happen when approximately [REDACTED] OS events are reached cumulatively in the 2 treatment groups. If OS early success is achieved in the IA (interim efficacy boundary specified in [Table 9-2](#) is crossed), the IA will serve the purpose of PA of OS.

If OS achieves statistical significance at the interim analysis, key secondary endpoints (PFS and PRO) will be tested.

Data will be subject to ongoing checks for integrity, completeness, and accuracy in accordance with the Data Management Plan with the expectation that outstanding data issues are resolved ahead of the lock to the extent possible. The data supporting the primary analysis will be locked to prevent further changes.

9.4.1.3 Final Analysis

The final analysis will occur when enrollment is complete and each subject completes the study, including LTFU. Data will be subject to ongoing checks for integrity, completeness, and accuracy in accordance with the Data Management Plan with the expectation that outstanding data issues are resolved ahead of the lock to the extent possible. The data supporting the final analysis will be locked to prevent further changes.

9.4.2 Methods of Analyses

9.4.2.1 General Considerations

Descriptive statistics will be provided for selected demographics, safety, PK, pharmacodynamics, and biomarker data. Descriptive statistics on continuous data will include means, medians, standard deviations, and ranges, while categorical data will be summarized using frequency counts and percentages. Graphical summaries of the data may also be presented.

The primary inferential comparisons of the OS primary endpoint between tarlatamab and SOC arms will be made using a stratified log-rank test controlling for the randomization stratification factors. The HR and its 95% CI will be estimated using a Cox proportional hazards model stratified by the randomization stratification factors. Stratum that is too small may be collapsed in the stratified log-rank analysis. The distribution of OS, including the median and quartiles and their corresponding 95% CIs will be characterized using the Kaplan-Meier method. Overall survival rates for selected landmarks (eg, 1 year and 2 years) will be reported with the 95% CI.

Progression free survival will be analyzed using the same approach as OS. The PFS rate at 1 year will be reported with the 95% CI.

The descriptive analysis of ORR will be provided using the Cochran-Mantel-Haenszel chi-square test controlling for the randomization stratification factors. An estimate of the common odds ratio (95% CI) will be provided as a measure of the relative treatment effect. The ORR will be calculated and the 95% CI will be estimated using the Clopper-Pearson Method.

The descriptive analysis of DOR will be provided using the same methods as OS.

The change from baseline over time to 18 weeks in symptoms of chest pain and cough will be measured by a single question from EORTC-QLQ-LC13 will be analyzed using generalized linear mixed model for repeated measures with cumulative logit link. The change from baseline over time to [redacted] weeks in symptoms of dyspnea will be measured by a multiple item dyspnea domain from EORTC-QLQ-C30 and EORTC-QLQ-LC13 Symptom Scores. The change from baseline over time to [redacted] weeks in physical functioning and global health status will be measured by QLQ-C30 Domain Scores. The inferential comparison will be made using a mixed model for repeated measurement (MMRM). Missing data for the MMRM will be handled under the assumption of missing at random (MAR). Further details of secondary endpoint testing will be described in the SAP.

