^f Local labs may be obtained within 48 hours prior to dose. Results must be reviewed prior to study drug administration.

^g TSH and FT4, lipase and amylase if obtained within 72 hours prior to dose. Results must be reviewed prior to study drug administration.

^h Q6W (every 6 weeks [\pm 7 days]) from C1D1, except where noted in the SoA for [REDACTED].

ⁱ Starting in cycle 4, collect predose PK samples only (up to 2 hours prior to start of infusion) every other cycle through Cycle 12 (C4, C6, C8, C10, C12).

Table 1-3. Standard of Care Schedule of Activities

Procedure ^a	SCR -21 to Day 0	Study Treatment (21-day [1+3 day] Cycles)					Q6W ^g	As Clinically Indicated	EOT	SFU ^b	LTFU ^c	NOTES
		0	1	2	3	4	5	8	15			
GENERAL AND SAFETY ASSESSMENTS												
Informed consent	X											
Eligibility	X											Eligibility criteria will be evaluated during screening and prior to randomization.
Medical History	X											Includes medical/surgical and cancer history.
Demographics	X											
Substance use history	X											Substances: alcohol, tobacco
Randomization	X											Subjects must initiate the first administration of study treatment by end of the third calendar day from randomization. This will serve as C1D1. Randomization should be registered once all other screening assessments have been completed.
Physical examination	(X)	[X]										Physical exam must be completed prior to dose administration on treatment days. (X): Height to be collected at screening only [X]: Must include weight and BSA BSA should be calculated during screening per Mosteller formula and utilized to calculate required study drug doses.
Neurological examination	X	X					X	X	X	X		Neurological exam must be completed prior to start of infusion on treatment days.
ECOG PS	X	X										
NYHA		X										Collect at screening only for subjects with known history of congestive heart failure to verify exclusion 207.
12-lead ECG		X					X	X				Single ECGs

Footnotes defined on last page of this table

Page 1 of 6

CONFIDENTIAL

Table 1-3. Standard of Care Schedule of Activities

Procedure ^a	SCR	Study Treatment (21-day [+3 day] Cycles)					Q6W ^g	As Clinically Indicated	EOT	SFU ^b	LTFU ^c	NOTES
Day	-21 to 0	1	2	3	4	5	8	15				
GENERAL AND SAFETY ASSESSMENTS (CONT.)												

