
 Compare the treatment effect of tarlatamab with SOC on Patient-reported disease-related symptoms, Physical Function, and Quality of Life 	
 Change from Baseline assessed 6-weekly over time to 18 weeks 
Chest Pain as measured by European Organization for Research and Treatment of Cancer Quality of Life Questionnaire Lung Cancer 13 (EORTC-QLQ-LC13)
 
Cough as measured by EORTC-QLQ-LC13
 
Dyspnea as measured by EORTC Cancer Quality of Life Questionnaire 30 (EORTC-QLQ-C30) and EORTC-QLQ-LC13
 
Physical Function as measured by EORTC-QLQ-C30
 
Global Health Status of life as measured by EORTC-QLQ-C30

Attributes	Key Secondary Estimand: PRO

 Target Population 	
 Subjects with relapsed small cell lung cancer after platinum-based first-line chemotherapy

 Key Secondary Endpoint 	
 Patient-reported outcome (PRO)

 Summary Measures 	
 Change from Baseline assessed 6-weekly over time to 18 weeks

 Intercurrent Events and Strategies 	
 Discontinuation of treatment PRO measurements before or on discontinuation of treatment will be used to estimate treatment effect (hypothetical strategy)
Key Secondary Estimand Description – PRO	

 Change from Baseline assessed 6-weekly over time to 18 weeks in PRO endpoints between tarlatamab and SOC, for subjects with relapsed small cell lung cancer after platinum-based first-line chemotherapy. PRO measurements before or on discontinuation of treatment will be used to estimate treatment effect (hypothetical strategy) 	
Secondary	

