6.4 Method of Treatment Assignment

Subjects will be randomized in a 1:1 allocation ratio, to receive tarlatamab or SOC therapy (lurbinectedin or topotecan in US, Canada, Australia, Singapore, Korea; amrubicin in Japan; or topotecan in all countries except Japan), respectively, in an open-label manner. For subjects randomized to the SOC arm in US, Canada, Australia, Singapore, and Korea, lurbinectedin or topotecan may be selected for treatment based on investigator discretion.

The stratification factors are:

- Prior anti-PD-(L)1 exposure (yes vs no)
- Chemotherapy-free interval (\geq 180 days, < 180 to \geq 90 days, or < 90 days)
- Presence (previous or current) of brain metastases (yes or no)
- Standard of care (topotecan/amrubicin vs lurbinectedin)

The randomization will be performed by IRT, and the randomization number will be provided to the site via IRT. The randomization date is to be documented in the subject's medical record and on the Subject Enrollment CRF (via IRT).

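### Chest pain and cough: a cumulative logit on change from baseline with no stated baseline term would lose power if run as written, and its odds ratio is not tied to the PRO estimand

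*Protocol*

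**What the plan says.** Chest pain and cough are key secondary endpoints, each taken from one EORTC-QLQ-LC13 question. Protocol Sections 9.4.2.1 and 9.4.2.2, and the Synopsis, make the change from baseline to week 18 the quantity that "will be analyzed using generalized linear mixed model for repeated measures with cumulative logit link". None of these places lists the model terms.

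Section 9.3.1 leaves covariates open: "Covariates may be incorporated in selected models of efficacy endpoints". Its list holds the stratification factors, region, best response on last prior therapy, demographics, disease features, ECOG and LDH. It has no baseline PRO score.

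The PRO estimand (Synopsis and Section 3) gives one summary measure for all five PRO endpoints: "Change from Baseline assessed 6-weekly over time to 18 weeks". The OS and PFS estimands, by contrast, name the hazard ratio.

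Section 9.1 places the two items under alpha control after OS and PFS: change from baseline "in 3 lung cancer symptoms including chest pain, cough, and dyspnea will be tested using Holm's procedure". Physical functioning and global health status can be tested only if all three symptom hypotheses are rejected.

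Section 9.4.2.1 leaves further detail to a SAP. The SAP supplied is an integrated safety plan covering three studies. It plans no hypothesis tests and contains no PRO analysis.

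**The concern.** The change in a bounded item depends on where the subject starts. Someone at the lowest level cannot improve, and someone at the highest cannot worsen. Without the baseline category in the model, that between-subject variation stays in the error and costs power. It also undermines the proportional-odds assumption. At the improvement cut-points, subjects who start at the floor count as not improved in both arms, which pulls the odds ratio there toward 1. One odds ratio across all change cut-points is then a poor summary even when the underlying effect is constant.

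The gate raises the stakes, because failure on either single item closes the tests of physical functioning and global health status. The model would also report an odds ratio for two endpoints and the MMRM would report mean differences for the others, under an estimand line that names neither.

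**Working it through.** **Inputs.** The Protocol gives the allocation ("Subjects will be randomized in a 1:1 allocation ratio", Section 6.4), one question per symptom, and 6-weekly assessment to week 18. It gives no PRO effect size, SD, correlation or power, so there is no stated figure to reproduce. Sample size and alpha are blacked out in the public text, and the number of LC13 response levels is not given. The following are therefore assumptions: 4 levels; latent shift 0.30 SD; latent baseline/follow-up correlation ρ of 0.4 to 0.8; two-sided 0.05; one post-baseline visit; baseline shares 25/40/25/10% (cough-like) and 60/25/10/5% (chest-pain-like).

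**Step 1: continuous analogue.** With unit SD at each time, the variance of change is 2(1−ρ) and the variance after baseline adjustment is 1−ρ². Their ratio, adjusted to change, is (1−ρ²)/[2(1−ρ)] = (1+ρ)/2. If n gives 80% power with adjustment, power for unadjusted change is Φ(√((1+ρ)/2) × (1.96+0.84) − 1.96).

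| ρ | (1+ρ)/2 | n ratio, change to adjusted | Power, unadjusted change |
|---|---|---|---|
| 0.4 | 0.70 | 1.43 | 65% |
| 0.5 | 0.75 | 1.33 | 68% |
| 0.6 | 0.80 | 1.25 | 71% |
| 0.8 | 0.90 | 1.11 | 76% |

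The loss is 4 points (80−76) to 15 points (80−65).

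**Step 2: ordinal simulation.** 150 per arm, 400 replicates, proportional-odds likelihood-ratio tests. One Monte Carlo SE is at most √(0.25/400) = 2.5 points.

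| Item, ρ | Logit on change, no baseline | Logit on change + baseline | Logit on category + baseline | Linear on change, no baseline |
|---|---|---|---|---|
| Cough-like, 0.4 | 51% | 77% | 75% | 53% |
| Cough-like, 0.6 | 69% | 85% | 85% | 71% |
| Cough-like, 0.8 | 85% | 92% | 91% | 85% |
| Chest-pain-like, 0.4 | 37% | 56% | 60% | 38% |
| Chest-pain-like, 0.6 | 47% | 68% | 70% | 47% |
| Chest-pain-like, 0.8 | 73% | 80% | 82% | 72% |

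Comparing unadjusted change with category given baseline, the loss runs from 6 points (91−85) to 24 points (75−51).

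**Step 3: second run, 360 subjects in total, same shift and range of ρ.** Chest-pain-like: 48–81% against 70–92%, a loss of 22 down to 11 points. Cough-like: 60–92% against 79–96%, a loss of 19 down to 4 points. Across all runs the range is 4 to 24 points.

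**Step 4: source of the loss.** On unadjusted change, the logit and linear columns agree within about 2 points, so the link costs nothing visible. Adding the baseline category to the change model recovers most or all of the gap.

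**Step 5: the gate.** All three symptoms must be rejected, so the gate cannot open more often than its weakest item rejects at the full level. At ρ = 0.6 that ceiling is 47% without baseline and 70% with category given baseline. Holm's earlier steps are stricter (0.05/3 = 0.0167 if total alpha were 0.05), so actual figures would be lower.

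**Step 6: common odds ratio.** With a constant 0.3 SD latent shift and ρ = 0.5, simulated odds ratios across change cut-points ran 1.30–2.40 (chest-pain-like) and 1.48–2.39 (cough-like). Modelling category given baseline narrowed this to about 1.7–2.4. Some spread is expected from reading a normal shift on the logit scale. At a central cut, Φ(0.3) = 0.618 gives 0.618/0.382 = 1.6. At a 2 SD cut, (0.0446/0.9554)/(0.0228/0.9772) = 2.0. At ρ = 0.5 the latent change has SD √(2×0.5) = 1, so the same benchmark applies to a change score without bounds, and its lowest value is about 1.6. Values of 1.3 to 1.5, which fall at the improvement cut-points, therefore reflect the floor.

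**The case against.** The strongest reply is that the Protocol names a model class and not a full specification. It lists no treatment, visit or interaction terms either, gives none for the MMRM, and defers detail to a study SAP due before database lock. This stands: a reader might infer that the sponsor has decided to omit baseline, and the documents do not support that. The power loss is conditional.

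The sentence in Section 9.4.2.1 is also garbled. It could mean that the ordinal item itself is modelled over time, with change read from the model. That reading is possible, but Section 9.4.2.2 makes the change the quantity analysed, and the covariate list omits the baseline score.

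Three other stronger inferences fail:

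- The cumulative logit is not itself wasteful; Step 4 shows that it matches a linear model.
- The estimand is not a mean change that the model fails to estimate. No mean is named; the gap is an unspecified summary measure.
- Nothing here shows an inflated type I error.

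On power alone, replacing change with category is not clearly better than adding baseline to the change model; the two are mostly within simulation error. The case for the category rests on floor, ceiling and interpretation. Part of the odds-ratio spread is a scale artefact, as Step 6 shows.

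Whether baseline should come from the screening or the cycle 1 day 1 questionnaire is a separate question that was not examined here.

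**Conclusion.** The point holds in conditional form. If the two items are analysed as Sections 9.4.2.1 and 9.4.2.2 read, with change as the response and no baseline term, each test loses roughly 4 to 24 points of power, most when the baseline/follow-up correlation is low. The direction was the same in every scenario run. The size depends on the assumed levels, sample size, effect, correlation, alpha and baseline distributions, and on a single visit without random effects, whereas the plan has repeated visits. The mismatch with the estimand does not depend on those assumptions: the line names no population-level contrast, so the odds ratio has no stated place in it. This is a free improvement, not a flaw that invalidates the tests.

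**What to change.** In Sections 9.4.2.1 and 9.4.2.2, and in the study SAP, state for chest pain and cough:

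- **Response:** the observed ordinal item category at weeks 6, 12 and 18.
- **Terms:** baseline item category, treatment, visit, treatment-by-visit and the randomization stratification factors. Name the questionnaire that supplies the baseline category.
- **Summary measure:** the cumulative odds ratio for a better category over weeks 6 to 18, entered in the PRO estimand for these two items. Say whether it is conditional on the random effects or population-averaged.

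If the sponsor prefers to keep change as the response, adding the baseline category recovers most of the power, but the floor and ceiling problem with a common odds ratio should then be acknowledged.

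The cost is a few lines of text and no extra data. Section 9.4.1.2 allows the PRO tests at the interim analysis if OS is significant there, so the wording should be fixed before the interim data are locked.
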